8.4 Vital signs, physical findings, and other observations related to safety

8.4.1 Vital signs

Vital signs will be measured in a semi-supine position after 5 minutes rest and will include:

- Systolic and diastolic blood pressure;
- Pulse rate;
- Oral body temperature;
- Respiratory rate.

On dosing visits (Days 1 and 15 of each cycle), vital signs on treatment days (i.e. on Days 1 and 15 of each cycle) will be assessed at multiple timepoints: predose, 10 minutes (± 5 minutes) and 30 minutes (± 10 minutes) after the start of the infusion, at the end of the infusion (+15 minutes); and at 1 hour (+15 minutes) after the end of the infusion. In addition, on Cycle 1 Day 1, vital signs will also be assessed at 2 hours (+1 hour) and 8 hours (+2 hours) after the end of the infusion, to correspond with PK sampling timepoints; vital signs measurements will be performed prior to the collection of PK samples.

At Screening and on non-treatment days (Days 2, 8, 16 and 22 of Cycle 1 and Day 8 of Cycle 2 and the SFU visit), vital signs will be measured once prior to collection of PK samples.

Observed vital sign measurements and changes from Baseline will be listed by visit and timepoint and summarized using descriptive statistics. In addition, for each of the vital signs, the Baseline value, the minimum, maximum, average and last post-Baseline value for each participant will be calculated based on all available scheduled postdose values during each cycle up to the predose value on Day 1 of the subsequent cycle and will be summarized by cycle using descriptive statistics. The last value in a cycle will be the predose value of the subsequent cycle where a subsequent cycle occurs, otherwise it will be the value at the last scheduled assessment. If only 1 value is available then the average will not be calculated and presented but this value will be used for the minimum, maximum and last post-Baseline summary measures. These summary measures for each cycle will also be listed.

For the multiple vital signs measurements on treatment days (i.e. on Days 1 and 15 of each cycle), changes from the predose value will be calculated at each postdose timepoint and summarized using descriptive statistics.

For each vital signs parameter, the mean (\pm standard deviation) change from Baseline value will be plotted over scheduled visit and timepoint with treatment group overlaid on the same plot.

The incidence of treatment-emergent markedly abnormal (TEMA)/potentially clinically significant (PCS) vital signs based on blood pressure and pulse rate measurements will be summarized by visit and timepoint using frequency counts and percentages. The criteria for identifying a TEMA/PCS are included in Table 8-2.

Table 8-2: TEMA/PCS Criteria for Vital Signs

Variable (unit)	Low ^a	High ^a
Systolic Blood Pressure (mmHg)	Value <90 and \geq 20 decrease from Baseline	Value >140 and \geq 20 increase from Baseline
Diastolic Blood Pressure (mmHg)	Value <50 and \geq 15 decrease from Baseline	Value >90 and \geq 15 increase from Baseline
Pulse Rate (bpm)	Value <45 and \geq 15 decrease from Baseline	Value >90 and \geq 15 increase from Baseline

bpm=beats per minute; PCS=potentially clinically significant; mmHg=millimeter of mercury; TEMA=treatment-emergent markedly abnormal.

^a Both conditions must be satisfied for a measurement to be considered PCS.

8.4.2 12-Lead Electrocardiograms

Electrocardiograms will be performed at each visit and timepoint in triplicate with the participant in a supine position after a minimum of 5 minutes rest.

On Days 1 and 15 of Cycle 1, ECGs will be performed in triplicate at multiple timepoints relative to the dose of study treatment (predose, end of infusion, and 8 hours after the end of infusion prior to PK sampling). On all other treatment days (Days 1 and 15 of all subsequent cycles of study treatment), ECGs will be performed in triplicate predose. At Screening and on non-treatment days, ECGs will be performed once in triplicate prior to PK sampling.

All ECGs will be evaluated for any clinically relevant changes by the investigator.

Electrocardiograms will also be collected for central reading, the data from which will be analyzed separately.

All summaries and listings of ECG data will be based on the local (site) 12-lead ECG measurements.

The following ECG parameters will be reported:

- PR interval;
- QT interval;
- QRS interval;
- QTcF interval (QT corrected for heart rate using Fridericia's formula [QTcF]);
- Heart rate.

Observed values and changes from Baseline in these ECG parameters will be listed and summarized by visit using descriptive statistics. The mean of the triplicate measurements taken for each parameter will be used in the summary at each visit and timepoint. If less than 3 of the triplicate measurements are taken then the mean of the available measurements will be used (if only 1 of the 3 triplicate measurements is available then this value will be used in the summaries). The Baseline value will be the mean of the last scheduled or unscheduled triplicate measurements taken prior to first dose of study treatment on Day 1 of Cycle 1. If no predose triplicate measurements are taken then the mean of the triplicate measurements taken at Screening will be used. The mean of only the scheduled triplicate measurements at each Post-Baseline visit and timepoint will be included in the summary. In addition, for each of the ECG parameters, the minimum, maximum, average and last post-Baseline value for each participant will be calculated based on the mean of the triplicate of all available scheduled postdose measurements during each cycle up to the predose value on Day 1 of the subsequent cycle, and will be summarized by cycle using descriptive statistics. The last value in a cycle will be the predose mean triplicate value of the subsequent cycle where a subsequent cycle occurs, otherwise it will be the mean triplicate value at the last scheduled assessment. If only 1 mean triplicate value is available then the average will not be calculated and presented but this value will be used for the minimum, maximum and last post-Baseline value summary measures. These summary measures for each cycle will also be listed.

For the multiple ECGs performed on Days 1 and 15 of Cycle 1, changes from the predose value will be calculated at each postdose timepoint and summarized using descriptive statistics.

Mean (\pm standard deviation) change from Baseline in QTcF will be plotted over scheduled visit with treatment groups overlaid on the same plot. Individual observed values of QTcF will be presented over actual time in a spaghetti plot.

The following cut-points in QTcF will be applied for observed data and changes from Baseline:

For observed QTcF data:

- <450 msec;
- ≥450 to <480 msec;
- ≥480 to <500 msec;

- ≥ 500 msec.

For changes from Baseline in QTcF:

- <30 msec;
- ≥ 30 to <60 msec;
- ≥ 60 msec.

The incidence of participants in each of these categories will be summarized using frequency counts and percentages by visit.

A listing of 12-lead ECG abnormal findings will be presented.

Electrocardiograms will also be collected for central reading; however, these data will be reported in an addendum to the CSR.

8.4.3 Echocardiogram

Echocardiograms will be performed at the Screening visit, on Day 1 of Cycles 2 and 3, and then on Day 1 of even cycles from Cycle 3 onwards.

All details on the echocardiogram assessments performed at each visit will be listed including the observed LVEF measurements and changes from Baseline, as well as information on whether the result was normal, abnormal NCS or abnormal CS.

Observed values and changes from Baseline in LVEF will be summarized by visit using descriptive statistics. In addition, shift tables for the change from Baseline in normal, abnormal NCS, abnormal CS LVEF results will be summarized by visit.

Mean (\pm standard deviation) change from Baseline in LVEF will be plotted over scheduled visit with treatment groups overlaid on the same plot. Individual observed LVEF results will be presented over actual time in a spaghetti plot.

8.4.4 ECOG performance status

ECOG performance status will be listed by participant and visit and will be summarized using frequency counts and percentages. A shift table summarizing the changes from Baseline to each post-Baseline visit will also be presented. Further detail on the ECOG performance scale, the listings and summaries are included in [Section 10.2](#).

8.4.5 Physical examination

Physical examination abnormalities from the complete physical examination performed at Screening and predose on Day 1 of Cycle 1, and from the symptom-directed physical examinations performed at other visits (predose on dosing visits), will be listed.

9 PHARMACOKINETICS AND PHARMACODYNAMICS

9.1 Pharmacokinetics

9.1.1 Secondary pharmacokinetic endpoint

The secondary PK endpoint for Part A of the study is the UCB6114 concentration in blood by time and dose.

UCB6114 concentrations will be listed for the SS and summarized using descriptive statistics by dose level (treatment group) and nominal (scheduled) sampling timepoints for the PKS (n, arithmetic mean, standard deviation, median, minimum, maximum, geoMean, geoCV and 95% CI for the geoMean [assuming lognormally distributed data]).

Listings of the UCB6114 concentration data will include the actual and nominal (scheduled) sampling times and any deviations between them. Deviations will be calculated relative to the start of the iv infusion. Any samples that are obtained outside the tolerance window permitted at the specified timepoint will be discussed at the DEM and any possible exclusion from the summaries will be documented accordingly.

Individual study participant UCB6114 concentration-time profiles and spaghetti plots of the individual concentration-time profiles for UCB6114 will be displayed graphically on the linear and semi-logarithmic scale. Geometric mean profiles of UCB6114 concentrations over nominal (scheduled) time will be presented with treatment group overlaid on the same plot, on both the linear and semi-logarithmic scale. The 95% CIs for the geoMean will be displayed on the linear scale plot only and the LLOQ will be included on all semi-logarithmic scale plots of UCB6114 concentrations.

[figure not shown]
Depending on the data, the UCB6114 concentration-time data may be subject to a population PK analysis using non-linear mixed effects modelling to characterize the disposition characteristics of UCB6114 in the current study. The influence of important variables such as body weight and ADA status on the population PK parameter estimates may be evaluated. These analyses will be described in a separate data analysis plan and reported separately.

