3.2 General study level definitions

3.2.1 Relative day and time

For each participant, the relative day of an event or assessment will be derived using the date of their first dose of study treatment as reference.

Relative days for an event or assessment occurring before the date of first dose are calculated as follows:

$$\text{Relative Day} = \text{Event/Assessment Date} - \text{Date of First Dose}$$

The relative day for an event or assessment occurring on the date of first dose is 1. The relative day for an event or assessment occurring on or after the first dose to the date of the last dose of study treatment will be calculated as follows:

$$\text{Relative Day} = (\text{Event/Assessment Date} - \text{Date of First Dose}) + 1$$

For events or assessments occurring after the date of the last dose, relative day will be prefixed with '+' in the data listings and will be calculated as follows:

$$\text{Relative Day} = \text{Event/Assessment Date} - \text{Date of Last Dose}$$

There is no relative Day 0. Relative day will not be calculated in cases where dates are partial and should be presented as "--" in the relevant data listing.

Relative time of TEAEs recorded on the day of infusion (Days 1 and 15 of each cycle) will be derived in minutes as follows using the infusion start time as reference:

$$\text{Relative Time of TEAE} = \text{Onset Time of TEAE} - \text{Start Time of Infusion}$$

Relative times of PK and PD sampling will be derived in hours using the end of infusion times on the day of dosing as reference, i.e. on Days 1 and 15 of each cycle:

$$\text{Relative Sampling Time} = \text{Sampling Time} - \text{End of Infusion Time}$$

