8.1 Extent of exposure

Details on study treatment administration on Day 1 and Day 15 of each cycle of study treatment will be listed. This listing will be split into two parts. The first part will include the start and stop dates and times of infusion, duration of infusion, infusion rate, whether the infusion was temporarily stopped/interrupted, whether the infusion was permanently discontinued and, if this was the case, whether the interruption or permanent discontinuation was due to an AE or other reason. The second part of this listing will include, for each visit, infusion site, total volume delivered, volume infused, planned total dose and total dose actually administered at infusion. In addition, the percentage of planned dose received, total dose administered across all cycles, the number of complete cycles of study treatment received and the total number of doses of study treatment received will be listed.

The percentage of planned dose received will be calculated for each study participant at each dosing visit within each cycle as follows:

$$\text{Percentage of Planned Dose Received} = 100 \times \frac{\text{Total Dose Administered}}{\text{Planned Total Dose}}$$

Actual duration of infusion will be calculated in minutes only for those study participants who did not have any temporary interruption(s) of their infusion using the infusion start and stop times and included on this listing. Length of interruption(s) will be calculated for those study participants who had temporary interruption(s) of their infusion.

Extent or duration of exposure will be calculated and summarized. Frequency counts and percentages for the number of complete cycles of study treatment received (1, 2, 3, 4, >4) and summary statistics for the total dose of study treatment received across all cycles, the total number of doses of study treatment received and the duration of exposure to study treatment will be presented.

Duration of exposure will be calculated in days as follows:

$$\text{Duration of Exposure} = (\text{Date of Last Dose} - \text{Date of First Dose}) + 30$$

Note that 30 days is added to this calculation to account for a participant's continued exposure to UCB6114 following their last dose of study treatment.

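### Part A SAP Section 9.1.1 measures PK sampling-time deviations from the start of infusion, while sampling times are defined from its end, so listed deviations are wrong when an infusion does not run to plan

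*SAP*

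**What the plan says.** Part A SAP Section 9.1.1 describes the concentration listings. They show actual and scheduled sampling times and the differences between them, and the reference is given as: "Deviations will be calculated relative to the start of the iv infusion". No exception is made for samples taken at or after the end of infusion. The next sentence reads: "Any samples that are obtained outside the tolerance window permitted at the specified timepoint will be discussed at the DEM". Any resulting exclusion from the summaries is to be documented.

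Elsewhere the same SAP uses the other end of the infusion:

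- Section 3.2.1: "Relative times of PK and PD sampling will be derived in hours using the end of infusion times on the day of dosing as reference". The formula there subtracts the end-of-infusion time from the sampling time.
- Section 8.4.1, on Cycle 1 Day 1 vital signs, adds measurements at 2 hours and at "8 hours (+2 hours) after the end of the infusion, to correspond with PK sampling timepoints".
- Section 8.4.2, on Cycle 1 ECGs, gives the times as "predose, end of infusion, and 8 hours after the end of infusion prior to PK sampling".

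Section 8.1 foresees that infusions may not run to plan. Its listing records "whether the infusion was temporarily stopped/interrupted" and whether the infusion was permanently discontinued, and the length of any interruption is calculated.

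**The concern.** A deviation should be the actual time minus the scheduled time, with both measured from the same event. Here the scheduled post-infusion times are anchored to the end of infusion and the deviation to its start. The two agree only when the infusion lasts exactly as long as planned. Start-referencing also needs a planned infusion duration, which the Part A SAP does not state.

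UCB6114 concentration by scheduled assessment is the secondary endpoint (Section 2.2.2.1), and it is summarized by nominal time. The deviation in Section 9.1.1 is the only one that section defines, and it comes immediately before the rule that sends out-of-window samples to the DEM. If that rule uses this deviation, the timing screen is distorted for participants whose infusions were interrupted, slowed or cut short. The false pass matters more than the false flag: a flagged sample is at least discussed, whereas a mistimed sample with a listed deviation of zero is not raised by this screen.

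**Working it through.** The plan gives no figure to reproduce, so the check is timing arithmetic.

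**Notation.** P is the planned infusion duration, d the actual minus planned duration, T the scheduled time after the end of infusion, and t the sample's true deviation from T. All are in minutes.

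**Deviation from the end of infusion (Section 3.2.1 reference).** (T + t) − T = t.

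**Deviation from the start of infusion (Section 9.1.1 reference).** (P + d + T + t) − (P + T) = t + d.

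P cancels, so the error is exactly d. For a window from 0 to +W, the start-referenced check accepts t from −d to W − d. The acceptance window moves earlier by d when the infusion is prolonged, and later when it is shortened.

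**Assumed inputs.** The PK windows are not in the document. I borrow the vital-sign tolerances in Section 8.4.1: end of infusion +15 minutes, 2 hours +60 minutes, 8 hours +120 minutes. That PK is sampled at the end of infusion is read from the ECG times in Section 8.4.2. The values of d are illustrative.

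| Timepoint (window) | d | In window but flagged | Out of window but passed |
|---|---|---|---|
| End of infusion (+15) | +5 | 11–15 late | 1–5 early |
| End of infusion (+15) | +30 | all (0–15 late) | 15–30 early |
| End of infusion (+15) | −10 | 0–9 late | 16–25 late |
| 2 h (+60) | +30 | 31–60 late | 1–30 early |
| 2 h (+60) | +90 | all (0–60 late) | 30–90 early |
| 8 h (+120) | +30 | 91–120 late | 1–30 early |

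For the −10 row, the accepted range is t from 10 to 10 + 15 = 25.

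**One case followed through (d = +45, 2-hour sample).**

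- Drawn exactly 2 hours after the actual end: t = 0, listed deviation 0 + 45 = +45. The listing is wrong, but +45 is inside +60, so the sample is not flagged.
- Drawn at the clock time implied by the planned duration: it falls 120 − 45 = 75 minutes after the actual end, so t = −45. The listed deviation is −45 + 45 = 0, and the sample passes as on time.

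**With the end of infusion as reference,** the deviation is t whatever the value of d, and infusion length causes no misclassification.

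**The case against.** The strongest reply is that the start-of-infusion sentence describes a listing column. The next sentence tests samples against the permitted window and does not say that the test uses that column. The windows and their reference may sit in the protocol. This stands: the link to the window check is an inference from adjacent sentences. The wrong listed deviation does not depend on it.

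Second, no sample is dropped automatically. Out-of-window samples are discussed, and Section 3.4 separately sends important dosing deviations, including interrupted and discontinued infusions, to the DEM for possible exclusion of concentration data. Infusion start and stop times are available there. This also stands and limits the consequence. It is not a full safeguard: that review concerns the dosing deviation and does not correct the sample-timing values, and an overrun not classed as an important deviation would not be caught.

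Three stronger readings are tempting, and the documents do not support them:

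- A reader might infer that any prolonged infusion causes misclassification. Any change in duration shifts the acceptance window, but whether a given sample is misclassified depends on d, the draw time and the tolerance. A sample drawn exactly on schedule is flagged only when the prolongation exceeds the plus tolerance.
- A reader might infer that a mean or geometric mean will be lost. Section 3.1 requires three values for summary statistics, and cohorts have 3 to 6 evaluable participants (Section 2.3). The loss would need exactly three values at a timepoint, a false flag, and a DEM decision to exclude despite having the infusion times.
- A reader might infer that the errors fall where concentrations change fastest. The document gives no concentration-time data to show this.

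**Conclusion.** The inconsistency is real and is not reconciled within the Part A SAP. Followed as written, the deviation listed for an end-of-infusion or post-infusion sample is wrong by the actual minus planned infusion duration, and correct only when that difference is zero. That much follows from the text and needs no assumption about windows.

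The further consequence is conditional: on-time samples may be flagged, and samples drawn too early after the actual end may pass without review. It requires that the window check uses the Section 9.1.1 deviation, and its extent depends on PK windows that are not shown. The minute ranges above are illustrative. No primary endpoint is affected, and the secondary-endpoint summaries change only if a sample is wrongly excluded or wrongly retained. Severity is minor. The point is confined to Part A, because the corresponding text of the Part A1 SAP is blacked out.

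**What to change.** Amend the sentence in Part A SAP Section 9.1.1 so that deviations for end-of-infusion and post-infusion samples are calculated relative to the actual end of infusion, consistent with Section 3.2.1, and deviations for predose samples relative to the start of infusion. It would help to add that the tolerance-window check uses this same deviation.

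The cost is one sentence in the SAP and one derivation in the PK dataset. The infusion start and stop times are already collected (Section 8.1), so no new data are needed.

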9.1.2 Exploratory pharmacokinetic endpoints

Where possible, key and other PK parameters will be derived by ICON PLC using noncompartmental analysis (NCA) performed using Phoenix WinNonlin® v8.0.0.3716 or higher (Certara L.P., Princeton, NJ, USA) and according to UCB's Guideline on Performing NCA Analysis version 1.0 dated 15 Nov 2017. An assessment of dose-proportionality will also be performed.

Key and other derived PK parameters are defined in Table 9-1.

Table 9-1: Pharmacokinetic Parameters

This table is completely redacted by a large black rectangular box.

9.2 Pharmacodynamics

The following exploratory PD and biomarker endpoints will be obtained from blood and urine samples which will be analyzed at a number of external laboratory vendors:

- Serum markers of bone turnover;
- Urinary markers of bone turnover;
- cGremlin-1;
- Serum protein/proteomic analysis;
- Transcriptomic analysis;
- Genetic analysis;
- CtDNA.

The impact of UCB6114 on bone turnover will be explored using the serum and urinary markers provided by the analytical laboratory. These markers will be listed for the SS and summarized descriptively over time for the PDS by dose level (treatment group), as described for the clinical laboratory parameters in Section 8.3. For each marker of bone turnover, the mean (\pm standard deviation) value and the mean (\pm standard deviation) change from Baseline value will be plotted over scheduled visit with treatment group overlaid on the same plot.

cGremlin-1 will be reported as concentration in blood by nominal (scheduled) assessment and dose level. Concentrations of cGremlin-1 will be listed for the SS and summarized for the PDS

using descriptive statistics by dose level (treatment group) and nominal (scheduled) sampling timepoints (n, arithmetic mean, standard deviation, median, minimum, maximum, geoMean, geoCV and 95% CI for the geoMean [assuming lognormally distributed data]). Changes from Baseline will also be summarized. Individual study participant cGremlin-1 concentration-time profiles will be displayed graphically in spaghetti plots and geoMean cGremlin-1 concentration and 95% CI will be plotted at each nominal (scheduled) timepoint with treatment group overlaid on the same plot.

Serum protein/proteomic analysis, transcriptomic analysis, genetic analysis and the analysis of the test results from the blood samples taken for ctDNA will be performed and reported separately outside of the CSR.

Hematoxylin and eosin (H & E) staining and immunohistochemistry (IHC) will be used to analyze any available historical tissue biopsy samples obtained prior to a participant's entry into the study (e.g. at the time of diagnosis).

Test results from the H & E staining and for target genes, phosphatase and tensin homolog (PTEN), Ki67 (cellular marker for proliferation in tumors), Gremlin-1, mothers against decapentaplegic homolog 4 (SMAD4) and fibroblast activation protein (FAP) will be listed by variable and sample analyzed (multiple tissue samples from a tumor biopsy may have been analyzed for a participant) for the SS. No summaries of these data will be generated due to the expected small numbers of historical biopsy samples analyzed for each dose level (treatment group).

The following key/component variables will be derived based on H & E staining, PTEN, Ki67, Gremlin-1 and FAP test results. No derived variables will be generated for SMAD4; only raw test results will be listed. Note that multiple tissue samples from a tumor biopsy may have been analyzed for a participant and therefore multiple test results will be presented in the listings.

H & E: Tissue Integrity (Percentage of Necrosis in Tumor Area)

In order to assess tissue integrity, percentage of necrosis in the tumor area will be categorized as ' $<20\%$ ' and ' $\geq 20\%$ '. If percentage of necrosis data are missing but other H & E staining and IHC data are available for a participant (i.e. the participant had historical tumor biopsy sample(s) analyzed), then the result will be categorized as 'Not Done'.

This categorical variable will be listed together with all other H & E test results.

PTEN: Tissue Sample Quality Control

The presence of staining of intrinsic control elements on the slides together with the level of staining intensity will be used to determine the tissue sample quality control.

If staining of intrinsic control elements on stained slides='YES' and staining intensity of intrinsic control elements on stained slides is 1, 2 or 3 then the tissue sample quality control is 'Good', otherwise if the staining intensity of intrinsic control elements=0 then the tissue sample quality

control is 'Questionable'. If staining of intrinsic control elements on stained slides='NOT PRESENT' then the tissue sample quality control is 'No staining present'. If both variables are missing but other IHC results are available (i.e. the participant had historical tumor biopsy sample(s) analyzed), then the result will be categorized as 'Not done'.

This categorical variable will be listed together with the presence/absence of staining of intrinsic control elements on the slides, the level of staining intensity, staining pattern, staining artifacts and any assay-specific comments. Since the percent of tumor cells with staining intensity 0/1/2/3 and the H-score (test results for which will be provided by the laboratory) are less relevant to assessing the quality control of the tissue sample, these raw test results will not be listed.

Ki67 – Proliferative Activity of the Tumor

In order to assess the proliferative activity of the tumor mass, cellular proliferation reflected by the number of Ki67-positive cell objects in the tumor region divided by the total number of cell objects in the tumor region will be categorized as '<=10%' or '>10%' with the latter category indicating an actively/moderately proliferating tumor. If the test result is 'NOT EVALUABLE' or missing but IHC results are available (i.e. the participant had historical tumor biopsy sample(s) analyzed), then the result will be categorized as 'Not done'.

This categorical variable will be listed together with all other Ki67 raw test results.

Gremlin-1: Cytoplasmic Histoscore

The cytoplasmic histoscore will be calculated as a weighted score based on the percentage of tumor cells with Gremlin-1 cytoplasmic staining intensity 1, 2 or 3 as follows:

$(1 \times \text{percent tumor cells with Gremlin-1 cytoplasmic staining intensity 1}) + (2 \times \text{percent tumor cells with Gremlin-1 cytoplasmic staining intensity 2}) + (3 \times \text{percent tumor cells with Gremlin-1 cytoplasmic staining intensity 3})$.

The cytoplasmic histoscore will be missing if the participant had a historical biopsy tumor sample analyzed but there are no test results for percent tumor cells with Gremlin-1 cytoplasmic staining intensity 1, 2 or 3.

The cytoplasmic histoscore will be listed together with all other Gremlin-1 raw test results.

FAP

From the image analysis of FAP-stained slides, the tumor will be classified into 2 regions: the cancer (CN) tumor region and the invasive margin (IM) region using a pre-established digital automated algorithm. The IM region is usually a small proportion of the whole tumor and, per standard procedures at the analytical laboratory, will be identified first. As a result, there is a risk that some parts of the CN tumor region may be inaccurately classified as part of the IM region, particularly in cases when the tumor is small. Therefore, instead of using the results for the

percentage of high, medium and low intensity FAP provided by the laboratory, a decision was made to back-calculate the areas of the CN tumor region and the IM region and add these together in order to re-calculate the percentage of high, medium and low intensity FAP in the whole tumor.

These back-calculated results and derived variables based on FAP test results are defined in Table 9-2.

Table 9-2: FAP Derived Variables

Variable No.	FAP Derived Variable	Description and Calculation
1 ^[a]	Total Analyzed Tumor Area (um ²)	
This is the total tumor area (um²) across the CN tumor region and the IM region and will be calculated as the sum of the areas of the CN tumor region (um²) and the IM region (um²) where a non-missing numeric test result is available for both the area of the CN tumor region and the area of the IM region. Note that, in cases where no IM region is defined, the area of the IM region will be recorded as 0 or 'NOT APPLICABLE', or may be missing. If the area of the IM region is recorded as 'NOT APPLICABLE' or is missing, then 0 will be assumed in this calculation and the total analyzed tumor area will be equal to the area of the CN tumor region.
 
This variable will be missing if both the areas of the CN tumor region and IM region are missing, or if one or both are 'NOT EVALUABLE' or 'NOT DIAGNOSTIC'.

2	Measured Area of Weakly Stained FAP in the CN Tumor Region (um ²)	
This is the back-calculated area of weakly stained FAP in the CN tumor region (weak positive) and will be calculated by multiplying the area of the CN tumor region (um²) and the relative area of weakly stained FAP in the CN tumor region (%) where a non-missing numeric test result is available for both the area of the CN tumor region and the relative area of weakly stained FAP in the CN tumor region.
 
This variable will be set to 0 if one or both are missing, 'NOT EVALUABLE' or 'NOT DIAGNOSTIC'.

3	Measured Area of Moderately Stained FAP in the CN Tumor Region (um ²)	
This is the back-calculated area of moderately stained FAP in the CN tumor region (moderate positive) and will be calculated by multiplying the area of the CN tumor region (um²) and the relative area of moderately stained FAP in the CN tumor region (%) where a non-missing numeric test result is available for both the area of the CN tumor region and the relative area of moderately stained FAP in the CN tumor region.

Variable No.	FAP Derived Variable	Description and Calculation
		This variable will be set to 0 if one or both are missing, ‘NOT EVALUABLE’ or ‘NOT DIAGNOSTIC’.
4	Measured Area of Strongly Stained FAP in the CN Tumor Region (um ²)	
This is the back-calculated area of strongly stained FAP in the CN tumor region (strong positive) and will be calculated by multiplying the area of the CN tumor region (um²) and the relative area of strongly stained FAP in the CN tumor region (%) where a non-missing numeric test result is available for both the area of the CN tumor region and the relative area of strongly stained FAP in the CN tumor region.
 
This variable will be set to 0 if one or both are missing, ‘NOT EVALUABLE’ or ‘NOT DIAGNOSTIC’.

5	Measured Area of Weakly Stained FAP in the IM Region (um ²)	
This is the back-calculated area of weakly stained FAP in the IM region (weak FAP-positive) and will be calculated by multiplying the area of the IM region (um²) and the relative area of weakly stained FAP in the IM region (%) where a non-missing numeric test result is available for both the area of the IM region and the relative area of weakly stained FAP in the IM region.
 
This variable will be set to 0 if one or both are missing, ‘NOT EVALUABLE’ or ‘NOT DIAGNOSTIC’.

6	Measured Area of Moderately Stained FAP in the IM Region (um ²)	
This is the back-calculated area of moderately stained FAP in the IM region (moderate FAP-positive) and will be calculated by multiplying the area of the IM region (um²) and the relative area of moderately stained FAP in the IM region (%) where a non-missing numeric test result is available for both the area of the IM region and the relative area of moderately stained FAP in the IM region.
 
This variable will be set to 0 if one or both are ‘NOT EVALUABLE’ or ‘NOT DIAGNOSTIC’.

7 ^[a]	Measured Area of Strongly Stained FAP in the IM Region (um ²)	
This is the back-calculated area of strongly stained FAP in the IM region (strong FAP-positive) and will be calculated by multiplying the area of the IM region (um²) and the relative area of strongly stained FAP in the IM region (%) where a non-missing numeric test result is available for both the area of the IM region and the relative area of strongly stained FAP in the IM region.
 
This variable will be set to 0 if one or both are missing, ‘NOT EVALUABLE’ or ‘NOT DIAGNOSTIC’.

Variable No.	FAP Derived Variable	Description and Calculation
8 ^[a]	Total FAP-Positive Tumor Area (um ²)	
This is the total FAP-positive area across the CN tumor region and the IM region (whole tumor) and will be calculated as the sum of component derived variables 2-7.
 
If all 6 component variables are 0 then this derived variable will be missing.

9 ^[a]	Total Measured Area of Weakly Stained FAP (um ²)	
This is the total weak FAP-positive area across the CN tumor region and the IM region (whole tumor) and will be calculated as the sum of component FAP derived variables 2 and 5.

10 ^[a]	Total Measured Area of Moderately Stained FAP (um ²)	
This is the total moderate FAP-positive area across the CN tumor region and the IM region (whole tumor) and will be calculated as the sum of component FAP derived variables 3 and 6.

11 ^[a]	Total Measured Area of Strongly Stained FAP (um ²)	
This is the total strong FAP-positive area across the CN tumor region and the IM region (whole tumor) and will be calculated as the sum of component FAP derived variables 4 and 7.

12 ^[a]	Total Relative Area of Weakly Stained FAP (%)	
This is the percentage of weak FAP expression across the CN tumor region and IM region (whole tumor) and will be calculated using component FAP derived variables 1 and 9 as
 $(\text{Total Measured Area Of Weakly Stained FAP} / \text{Total Analyzed Tumor Area}) \times 100$ 
If the total analyzed tumor area is missing then this variable cannot be calculated and will be missing.

13 ^[a]	Total Relative Area of Moderately Stained FAP (%)	
This is the percentage of moderate FAP expression across the CN tumor region and IM region (whole tumor) and will be calculated using component FAP derived variables 1 and 10 as
 $(\text{Total Measured Area Of Moderately Stained FAP} / \text{Total Analyzed Tumor Area}) \times 100$ 
If the total analyzed tumor area is missing then this variable cannot be calculated and will be missing.

14 ^[a]	Total Relative Area of Strongly Stained FAP (%)	
This is the percentage of strong FAP expression across the CN tumor region and IM region (whole tumor) and will be calculated using component FAP derived variables 1 and 11 as

Variable No.	FAP Derived Variable	Description and Calculation
		(Total Measured Area Of Strongly Stained FAP / Total Analyzed Tumor Area) x 100 If the total analyzed tumor area is missing then this variable cannot be calculated and will be missing.
15 ^[a]	Total Relative FAP-Positive Tumor Area (TPS) (%)	This is the total proportion score which is the percentage of FAP-positive area across the CN tumor region and the IM region (whole tumor) and will be calculated using component derived variables 1 and 8 as (Total FAP-Positive Tumor Area / Total Analyzed Tumor Area) x 100 If the total analyzed tumor area is missing then this variable cannot be calculated and will be missing.
16 ^[a]	Total FAP Histoscore	This is a histoscore for the combined CN tumor region and IM region (whole tumor) and will be calculated as a weighted score based on component derived variables 12, 13 and 14 as (1 x Total Relative Area of Weakly Stained FAP) + (2 x Total Relative Area of Moderately Stained FAP) + (3 x Total Relative Area of Strongly Stained FAP)

CN=cancer; FAP=fibroblast activation protein, IM=invasive margin, TPS=total proportion score.

^[a] Included in the listing of FAP test results.

The derived variables containing the ^[a] flag in Table 9-2 above will be listed together with information on staining artifacts and any assay-specific comments provided by the laboratory.

Further informal analyses may be performed to explore the relationship between the PD and biomarker endpoints with antitumor activity, ADA status, and also with key PK parameters. The PK-PD effects of UCB6114 may be assessed using a population analysis approach. These analyses will also be performed separately outside of the CSR and the details of analysis methods will be included in a separate analysis plan.

The incidence of available historical tumor biopsies will be summarized by treatment group. The incidence of PD samples taken from blood and urine will be summarized by cycle and treatment group.

